12. INTERIM ANALYSES AND DATA MONITORING

There is no plan to establish a data monitoring committee for this study.

There are no formal interim analyses planned, however the HidroQoL assessment was evaluated upon enrollment of 100 eligible subjects. The treatment groups were not blinded. The mean, standard deviation, median, minimum, maximum and the same summary statistics for change from baseline for the HidroQoL total score, Daily Life Activities Domain score, and Psychosocial Life Domain score were reported using the HQL Population. The results of this analysis are intended to be used to inform protocol development for subsequent studies.

Version: 1.0 Page 32 of 51

13. CHANGES TO THE ANALYSES PLANNED IN THE PROTOCOL

Analyses specified in the protocol dated 6 May 2019 that have changed in this SAP include the following:

- Protocol Synopsis
 - The synopsis describes the baseline of HDSM-Ax as the average of Screening and Day 0. The baseline definition has been updated to be the Day 1 visit.
- Protocol Section 10.1 Analysis Populations
 - The definition of ITT population has been updated to include all subjects who were randomized.
- Protocol Section 10.2 Endpoints
 - For the exploratory efficacy endpoint, the protocol describes an interim analysis. It has been clarified in this SAP that the interim analysis was not formal and that the treatment groups were not blinded.
 - Endpoints have been added to the 'Other Efficacy Endpoint' section to capture the 11-item total of HDSM-Ax and the 7-item total of HDSM-Ax.
- Protocol Section 10.3 Safety Analysis
 - The protocol describes three sets of AE tables to be produced at each visit. The first set "(a) TEAEs reported at the current visit by those making the visit" will not be generated, as it will not provide any substantial information to the safety profile".
 - The protocol states that all SAEs will be summarized by the three sets of AE tables. Due to an expected low incidence, one SAEs table and one treatment-related SAEs table will be generated for all data through Week 52.

Version: 1.0 Page 33 of 51

Statistical Analysis Plan 24 February 2020

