Sofpironium bromide was safe and well tolerated. All three, 5%, 10% and 15% dose groups have demonstrated comparable acceptability of safety and tolerability. TEAEs were dose-related with fewer subjects reporting AEs in the 5% dose group relative to 10% and 15% gel groups.

Consistent with the soft drug design, sofpironium bromide gel exhibited low incidence of anticholinergic AEs. The most common anticholinergic AE was dry mouth. All anticholinergic AEs were expected. Of note, the anticholinergic AEs were predominantly mild or moderate in severity and transient in duration. Of the application site AEs reported by Investigators (erythema, pain, dryness) and local tolerability signs reported by subjects (burning and itching), most were minimal in severity. All TEAEs resolved spontaneously with treatment discontinuation.

Overall Efficacy Conclusions

All three, 5%, 10% and 15% sofpironium bromide dose groups exhibited a larger absolute mean reduction in GSP from baseline to EOT compared to vehicle. Better improvement in GSP response was associated with higher

concentrations of sofpironium bromide. However, while there was a slight trend toward dose-response, all dose groups were essentially equivalent in patient-reported outcome measures based on HDSM-Ax, HDSS, and DLQI. This suggests that each of the concentrations are efficacious. The response was seen as early as Day 8 and remained consistent throughout the applicable treatment period.

Overall Pharmacokinetics Conclusions

There was systemic exposure to both sofpironium and BBI-4010 analytes in the majority of subjects. Systemic exposure to sofpironium bromide appeared to increase in an approximately dose proportional manner between the 5% and 15% gel concentrations, indicating that applying a more concentrated gel increased exposure. However, inter-subject variability of PK parameters was extremely high. Absorption is thought to be affected by skin thickness, temperature, hydration, and degree of occlusion.

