9.2.1.2 Assessment of Adverse Events

For each AE, the start and resolution dates, intensity, seriousness (i.e., whether the event meets the definition of an SAE (Section 9.3.1), relationship of the event to the study drug, action taken regarding study drug, and outcome of the event will be documented on the eCRF.

Intensity

The following definitions should be used to assess and grade AE intensity, including laboratory abnormalities judged to be clinically significant.

Page 38 of 74

Severity Grade		Description
Mild	1	Awareness of sign or symptom, but easily tolerated
Moderate 2		Discomfort enough to cause interference with usual activity
Severe	3	Incapacitating with inability to work or do usual activity

Note: a severe adverse event is not necessarily serious.

Relationship

The relationship of an AE to study drug should be assessed using the guidelines presented in the table below. An AE for which there has been no causal relationship reported will require follow-up to determine causality.

Degree of Certainty	Description
Definitely Related	An event that follows a reasonable temporal sequence from administration of the test article; that follows a known or expected response pattern to the test article; and that is confirmed by improvement on stopping or reducing the dosage, and reappearance of the event on repeated exposure (re-challenge).
Probably Related	An event that follows a reasonable temporal sequence from administration of the test article; that follows a known or expected response pattern to the test article; and that is confirmed by improvement on stopping or reducing the dosage of the test article; and that is unlikely to have been caused by concurrent/underlying illness or other drugs, procedures, or other causes.
Possibly Related	An event that follows a reasonable temporal sequence from administration of the test article; that follows a known or expected response pattern to the test article; but may have been caused by concurrent/underlying illness, other drug, procedure, or other causes.
Unlikely Related	An event that does not follow a reasonable temporal sequence from administration of the test article; that does not follow a known or expected response pattern to the test article, or most likely was caused by concurrent/underlying illness, other drug, procedure, or other causes, because of their known effects.
Not related	An event almost certainly caused by concurrent/underlying illness, other drug, procedure, or other causes.

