10.3 Safety Analyses

Safety variables are local tolerability assessments, AEs, laboratory evaluations, and vital signs.

At each post-screening visit, local tolerability (burning, itching, scaling, dryness, and erythema at either axilla) will be tabulated by severity. At each post-baseline visit, local tolerability will also be summarized as cumulative shift tables vs. baseline. Subject counts for each symptom will be cross tabulated by baseline severity and the maximum post baseline severity reported for either axilla up to the current visit.

Adverse events will be coded from the verbatim text into preferred term (PT) and primary system organ class (SOC) using the most current version of Medical Dictionary for Regulatory Activities (MedDRA). At each postbaseline visit, treatment-emergent adverse events (TEAEs, i.e., AEs occurring during or after treatment initiation) will be summarized in the following tables: all reported AEs, all treatment-related AEs, all SAEs, and AEs leading to investigational product discontinuation. Three sets of the above tables will be produced at each visit: (a) for TEAEs reported at the current visit by those making the visit, (b) for cumulative TEAEs up to the current visit reported by those making the visit, and (c) for cumulative TEAEs up to the current visit reported by all enrolled patients (including those absent from the current visit). For each TEAE, a patient will appear at most once by the highest severity reported.

Laboratory parameters will be descriptively summarized (mean, SD, median, minimum, maximum) for values at each visit and for changes from screening at each subsequent visit. In addition, at each post-screening visit, parameter status (low, normal, high) will also be summarized as shift tables vs. screening status.

Vital signs will be descriptively summarized (mean, SD, median, minimum, maximum) for values at each visit and for changes from screening at each subsequent visit.

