9.4 Adverse Events

Treatment-emergent adverse events (TEAEs) are defined as those adverse events (AEs) with onset after the first dose of study drug or existing events that worsened after the first dose during the study. Treatment-emergent AEs will be summarized by treatment group. Partial or missing start or end dates will be imputed per Section 9.1.1.

Verbatim terms on case report forms will be mapped to preferred terms and system organ classes using the latest version of MedDRA.

At Weeks 2, 4, 6, 12, 24, 48 and 52, treatment-emergent adverse events (TEAEs, i.e., AEs occurring during or after treatment initiation) will be summarized in the following tables: all reported TEAEs, all treatment-related TEAEs, severe TEAEs, TEAEs leading to dose interruption, TEAEs leading to dose modification, TEAEs leading to study discontinuation, TEAEs of special interest, and anticholinergic TEAEs. Two sets of the above tables will be produced: (a) for cumulative TEAEs up to the current visit reported by those making the visit, and (b) for cumulative TEAEs up to the current visit reported by all Safety Population subjects (including those absent from the current visit). At each of the 7 indicated weeks, each of the above tables will summarize the subject incidence (frequency count and %) for the specified TEAE, mapped to MedDRA System Organ Class and Preferred Term, according to the highest severity reported. Subjects with only unknown severity for a TEAE will be counted under the severity unknown category. Additionally, serious TEAEs and treatment-related serious TEAEs will be summarized in the same manner for all data through Week 52.

Version: 1.0 Page 26 of 51

Summaries that are displayed by system organ class and preferred terms will be ordered by descending incidence of system organ class in the combined BBI-4000 group and preferred term within each system organ class. The combined BBI-4000 group will not be displayed and will only be used for sorting. TEAEs of special interest include the following:

- Vision blurred
- Mydriasis
- Urinary hesitation
- Pupils unequal

Adverse event data will be presented in data listings by subject, treatment group, and event. Serious TEAEs and TEAEs leading to discontinuation of the study will be presented in separate data listings. Death is not expected. However, should death occur on study, the event will be reported with detailed narratives.

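### With the current-visit AE tables dropped in SAP 13, no planned summary table is described as showing whether systemic anticholinergic and special-interest events resolve, persist or recur over 48 weeks

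*SAP*

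**What the plan says.** Protocol 10.3 plans three TEAE sets at each visit after baseline. Set (a) is "for TEAEs reported at the current visit by those making the visit". Set (b) is cumulative among subjects who attend. Set (c) is "for cumulative TEAEs up to the current visit reported by all enrolled patients". Below they are called the current-visit, attendee-cumulative and all-subject-cumulative sets, because SAP 9.4 re-letters the two it keeps.

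SAP 13 states that the current-visit set "will not be generated, as it will not provide any substantial information to the safety profile". SAP 9.4 then reads: "Two sets of the above tables will be produced: (a) for cumulative TEAEs up to the current visit reported by those making the visit", and the second set is cumulative for the whole Safety Population. The timing is "At Weeks 2, 4, 6, 12, 24, 48 and 52, treatment-emergent adverse events" being tabulated by system organ class and preferred term, with each subject placed at the highest severity reported. Serious TEAEs are tabulated once, over all data to Week 52.

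The information needed to describe duration is collected. Protocol 9.2.1.2 begins its list of recorded items with "For each AE, the start and resolution dates, intensity". Local tolerability is handled separately: SAP 9.5 summarises severity at each visit, and SAP 15 lists Table 14.3.6.2 for this.

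**The concern.** The primary objective is long-term safety. Where Protocol 1 gives a treatment duration for the earlier repeat-dose studies, it is 14 to 42 days. On that experience the protocol says that "the anticholinergic AEs were predominantly mild or moderate in severity and transient in duration", and that TEAEs cleared once treatment stopped. Clearing after stopping does not show what happens when a subject keeps applying the gel for 48 weeks. A long-term trial can add that answer for dry mouth, which Protocol 1 calls the most common anticholinergic event, and for the four special-interest terms in SAP 9.4 (blurred vision, mydriasis, urinary hesitation, unequal pupils).

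A cumulative table counts a subject from the first occurrence and never removes the count. It therefore cannot separate an event that fades in a week from one that lasts for the whole treatment period. If every by-week table is cumulative, the study report could repeat or drop the word transient with no summary by arm behind either choice.

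**Working it through.** There is no sample size, power or test to reproduce: SAP 2.6 reports no formal calculation and SAP 3.1 plans no tests. The check is a table count followed by the SAP counting rule applied to two event histories.

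**1. Table count.** SAP 9.4 gives 7 weeks, 8 event groups (all, treatment-related, severe, leading to interruption, leading to modification, leading to study discontinuation, special interest, anticholinergic) and 2 sets.

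- Implied: 7 x 8 x 2 = 112.
- Listed in SAP 15: Tables 14.3.1.4.1 to 14.3.1.10.16, 16 for each of 7 weeks: 7 x 16 = 112. The two agree, and every title says cumulative to the stated week.
- Adding 14.3.1.1 (overall summary) and 14.3.1.2 and 14.3.1.3 (serious events) gives 115 AE tables. No title names duration, resolution, recurrence or ongoing status. For 14.3.1.1 only the title is available.

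**2. Two histories under the counting rule.** Inputs: 200 subjects on 15% gel (SAP 2.3); an assumed 10% with one event starting on Day 5, so 0.10 x 200 = 20 subjects; resolution on Day 10 (brief) or Day 336 = 48 x 7 (lasting); same term, severity, relatedness and action taken; nobody leaves. Nominal visit day = 7 x week. The current-visit rows look back to the previous scheduled visit.

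| Display | History | Wk 2 | 4 | 6 | 12 | 24 | 48 | 52 |
|---|---|---|---|---|---|---|---|---|
| All-subject cumulative | Brief | 20 | 20 | 20 | 20 | 20 | 20 | 20 |
| All-subject cumulative | Lasting | 20 | 20 | 20 | 20 | 20 | 20 | 20 |
| Current-visit, any event present since last visit | Brief | 20 | 0 | 0 | 0 | 0 | 0 | 0 |
| Current-visit, any event present since last visit | Lasting | 20 | 20 | 20 | 20 | 20 | 20 | 0 |
| Current-visit, new onsets only | Brief | 20 | 0 | 0 | 0 | 0 | 0 | 0 |
| Current-visit, new onsets only | Lasting | 20 | 0 | 0 | 0 | 0 | 0 | 0 |

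The cumulative rows read 20/200 = 10.0% at all seven weeks for both histories, a difference of zero. At 5% and 20% assumed incidence the entries become 10 and 40 and the pattern is unchanged, because the rule contains no duration term.

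**3. What differencing recovers.** The all-subject set has a fixed denominator, so the Week 4 count minus the Week 2 count gives first occurrences in that interval: 20 - 20 = 0 for both histories. This yields timing of first onset, including late onset. It does not yield persistence or recurrence.

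**4. Attrition.** The plan randomises up to 200 subjects on 15% gel to obtain about 100 completers, so half may leave. Suppose 20 of 200 have a lasting event and 100 remain at Week 48. If half of the affected subjects remain, prevalence is 10/100 = 10%. If all 20 have left, it is 0/100 = 0%, although no event resolved on treatment. A by-visit percentage therefore needs the discontinuations shown beside it.

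**5. End dates.** SAP 9.1.1 applies one imputation rule to start and end dates, and a completely missing date becomes the treatment start date. Read literally, an event that begins on Day 5 and is still ongoing would be given an end on Day 1, before its onset. A duration summary cannot use that rule.

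**The case against.** The strongest reply is that much of the needed information is already planned, and that the deleted set was never a duration analysis.

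- **Application-site reactions.** A reader might infer that these too cannot be followed over time. The documents do not support that. SAP 9.5 and Table 14.3.6.2 give severity by visit without cumulation. Under Protocol 8.1.3, local signs become AEs only if they need therapy, interruption or discontinuation. This stands, and confines the point mainly to systemic events.
- **Late onset.** A reader might infer that late-starting events are hidden. They are not: differencing the all-subject tables recovers first onset.
- **The deletion as sole cause.** A reader might infer that restoring the current-visit set would cure the problem. It depends on what counts as reported at a visit. If only new onsets count, brief and lasting events still look alike.
- **Identical in every AE table.** This is too strong. A lasting event may also be graded severe or lead to interruption, modification or discontinuation, and so enter other tables. Its duration would still not show.
- **Listings and later analyses.** SAP 17 lists all AEs and special-interest AEs, SAP 9.1.1 keeps the collected dates in listings, and SAP 1 allows supplementary analyses in the study report. This is true, but a listing gives no summary by arm, and an analysis chosen after database lock is weaker than one specified now.

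The change is documented and the study is descriptive, so no planned estimate becomes wrong. The missing summary of persistence for systemic events remains.

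**Conclusion.** The point holds for systemic anticholinergic and special-interest TEAEs. SAP 13 removes the only AE set tied to the current visit. All 112 by-week tables that remain count two events the same if they differ only in duration. No planned summary table is titled or described as showing whether such events resolve, persist or recur during 48 weeks of use, although start and resolution dates are collected.

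This rests on three conditions. The two events must share term, severity, relatedness and action taken. Table 14.3.1.1 is judged by its title, since table specifications are in a separate document. The protocol supplied is Amendment 01 while the SAP cites Amendment 4, but SAP 13 describes the same current-visit set. The 10% incidence is an illustration; the equality of the cumulative counts does not depend on it.

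**What to change.** Amend SAP 9.4, 13 and 15. For anticholinergic and special-interest TEAEs, by arm and with the same term lists as the existing tables, add:

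1. **A point-prevalence table.** At each listed visit, give the number and percentage of subjects with an event ongoing on the visit date, among those still in follow-up. Beside it, show how many had already discontinued and how many of those did so because of that event. Using the visit date avoids the unequal gaps between the listed weeks (2, 2, 2, 6, 12, 24 and 4 weeks), which would inflate counts over longer intervals.
2. **A duration summary.** Give the median and range in days for resolved events, the number ongoing at last contact, and the number of subjects with more than one episode. This also captures short events that fall between visits.

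State that in these tables an AE with no end date is treated as ongoing at last contact, and that the SAP 9.1.1 imputation of partial or missing dates is not applied to AE end dates. Restoring the current-visit set as worded may not be enough.

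The cost is about two extra table programs and one end-date rule, using data already collected, and a slightly longer table package.

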14. REFERENCES

International Conference on Harmonization of Technical Requirements for Registration of Pharmaceuticals for Human Use. Statistical principles for clinical trials (E9). International Conference on Harmonization; 1998.

Version: 1.0 Page 34 of 51

15.LIST OF PLANNED TABLES

Number	Title	Population
		All Randomized
14.1.1.1	Summary of Subject Disposition	Subjects
14.1.1.2	Summary of Major Protocol Deviations	Safety
14.1.2.1	Summary of Demographic Characteristics	Safety
14.1.2.2	Summary of Demographic Characteristics	ITT
14.1.2.3	Summary of Demographic Characteristics	Per Protocol
14.1.3.1	Summary of Baseline Characteristics	Safety
14.1.3.2	Summary of Baseline Characteristics	ITT
14.1.3.3	Summary of Baseline Characteristics	Per Protocol
14.1.4	Summary of Medical History	Safety
14.1.5	Summary of Prior Medications by Drug Class and Generic Drug Name	Safety
14.2.1.1.1	Proportion of Subjects Achieving ≥1-point Improvement in HDSM-Ax-11 from Baseline to End of Treatment	ITT
14.2.1.1.2	Proportion of Subjects Achieving ≥1-point Improvement in HDSM-Ax-11 from Baseline to End of Treatment	Per Protocol
14.2.1.2.1	Proportion of Subjects Achieving ≥1.5-point Improvement in HDSM-Ax-11 from Baseline to End of Treatment	ITT
14.2.1.2.2	Proportion of Subjects Achieving ≥1.5-point Improvement in HDSM-Ax-11 from Baseline to End of Treatment	Per Protocol
14.2.1.3.1	Proportion of Subjects Achieving ≥2-point Improvement in HDSM-Ax-11 from Baseline to End of Treatment	ITT
14.2.1.3.2	Proportion of Subjects Achieving ≥2-point Improvement in HDSM-Ax-11 from Baseline to End of Treatment	Per Protocol
14.2.1.4.1	Change from Baseline in HDSM-Ax-11 to End of Treatment	ITT
14.2.1.4.2	Change from Baseline in HDSM-Ax-11 to End of Treatment	Per Protocol
14.2.2.1.1	Proportion of Subjects Achieving ≥1-point Improvement in HDSM-Ax-7 from Baseline to End of Treatment	ITT
14.2.2.1.2	Proportion of Subjects Achieving ≥1-point Improvement in HDSM-Ax-7 from Baseline to End of Treatment	Per Protocol
14.2.2.2.1	Proportion of Subjects Achieving ≥1.5-point Improvement in HDSM-Ax-7 from Baseline to End of Treatment	ITT
14.2.2.2.2	Proportion of Subjects Achieving ≥1.5-point Improvement in HDSM-Ax-7 from Baseline to End of Treatment	Per Protocol
14.2.2.3.1	Proportion of Subjects Achieving ≥2-point Improvement in HDSM-Ax-7 from Baseline to End of Treatment	ITT
14.2.2.3.2	Proportion of Subjects Achieving ≥2-point Improvement in HDSM-Ax-7 from Baseline to End of Treatment	Per Protocol
14.2.2.4.1	Change from Baseline in HDSM-Ax-7 to End of Treatment	ITT
14.2.2.4.2	Change from Baseline in HDSM-Ax-7 to End of Treatment	Per Protocol
14.2.2.5.1	Proportion of Subjects Achieving ≥1-point Improvement in HDSM-Ax-11 from Baseline by Visit	ITT

Version: 1.0 Page 35 of 51

	Proportion of Subjects Achieving ≥1-point Improvement in	
14.2.2.5.2	HDSM-Ax-11 from Baseline by Visit	Per Protocol
	Proportion of Subjects Achieving ≥1.5-point Improvement in	
14.2.2.6.1	HDSM-Ax-11 from Baseline by Visit	ITT
142262	Proportion of Subjects Achieving \(\geq 1.5\)-point Improvement in	Dan Duata and
14.2.2.6.2	HDSM-Ax-11 from Baseline by Visit Proportion of Subjects Achieving ≥2-point Improvement in	Per Protocol
14.2.2.7.1	HDSM-Ax-11 from Baseline by Visit	ITT
11.2.2.7.1	Proportion of Subjects Achieving \(\geq 2\)-point Improvement in	
14.2.2.7.2	HDSM-Ax-11 from Baseline by Visit	Per Protocol
	Proportion of Subjects Achieving ≥1-point Improvement in	
14.2.2.8.1	HDSM-Ax-7 from Baseline by Visit	ITT
14000	Proportion of Subjects Achieving ≥1-point Improvement in	D D 1
14.2.2.8.2	HDSM-Ax-7 from Baseline by Visit	Per Protocol
14.2.2.9.1	Proportion of Subjects Achieving ≥1.5-point Improvement in HDSM-Ax-7 from Baseline by Visit	ITT
14.2.2.3.1	Proportion of Subjects Achieving ≥1.5-point Improvement in	11 1
14.2.2.9.2	HDSM-Ax-7 from Baseline by Visit	Per Protocol
	Proportion of Subjects Achieving \(\geq 2\)-point Improvement in	
14.2.2.10.1	HDSM-Ax-7 from Baseline by Visit	ITT
	Proportion of Subjects Achieving ≥2-point Improvement in	
14.2.2.10.2	HDSM-Ax-7 from Baseline by Visit	Per Protocol
14.2.2.11.1	Change from Baseline in HDSM-Ax-11 by Visit	ITT
14.2.2.11.2	Change from Baseline in HDSM-Ax-11 by Visit	Per Protocol
14.2.2.12.1	Change from Baseline in HDSM-Ax-7 by Visit	ITT
14.2.2.12.2	Change from Baseline in HDSM-Ax-7 by Visit	Per Protocol
14.2.2.13.1	Change from Baseline in DLQI by Visit	ITT
14.2.2.13.2	Change from Baseline in DLQI by Visit	Per Protocol
14.2.2.14.1	Patient Global Impression - Severity (PGI-S) by Visit	ITT
14.2.2.14.2	Patient Global Impression - Severity (PGI-S) by Visit	Per Protocol
	Patient Global Impression - Severity (PGI-S) Shift from	
14.2.2.15.1	Baseline to Each Visit	ITT
	Patient Global Impression - Severity (PGI-S) Shift from	
14.2.2.15.2	Baseline to Each Visit	Per Protocol
14.2.2.16.1	Patient Global Impression of Change (PGI-C) by Visit	ITT
14.2.2.16.2	Patient Global Impression - Change (PGI-C) by Visit	Per Protocol
14.2.3	Change from Baseline in HidroQoL by Visit	HQL
14.3.1.1	Overall Summary of Treatment Emergent Adverse Events	Safety
	Number and Percentage of Subjects with Serious Treatment-	
	Emergent Adverse Events by System Organ Class, Preferred	
14.3.1.2	Term, and Maximum Severity	Safety
	Number and Percentage of Subjects with Serious Treatment-	
14.3.1.3	Related Treatment-Emergent Adverse Events by System Organ Class, Preferred Term, and Maximum Severity	Safety
1 T .J.1.J	Organ Class, referred refin, and waximum severity	Barety

Version: 1.0 Page 36 of 51

	N I D f C. l.: idl. T t F t	
	Number and Percentage of Subjects with Treatment-Emergent	C-f-4 (C-1-:4-
142141	Adverse Events Cumulative to Week 2 by System Organ	Safety (Subjects
14.3.1.4.1	Class, Preferred Term, and Maximum Severity	Reaching Week 2)
		Safety (All Safety
	Number and Percentage of Subjects with Treatment-Emergent	Subjects,
	Adverse Events Cumulative to Week 2 by System Organ	Reaching Week 2
14.3.1.4.2	Class, Preferred Term, and Maximum Severity	or Not)
	Number and Percentage of Subjects with Treatment-Related	
	Treatment-Emergent Adverse Events Cumulative to Week 2	
	by System Organ Class, Preferred Term, and Maximum	Safety (Subjects
14.3.1.4.3	Severity	Reaching Week 2)
	Number and Percentage of Subjects with Treatment-Related	Safety (All Safety
	Treatment-Emergent Adverse Events Cumulative to Week 2	Subjects,
	by System Organ Class, Preferred Term, and Maximum	Reaching Week 2
14.3.1.4.4	Severity	or Not)
	Number and Percentage of Subjects with Severe Treatment-	,
	Emergent Adverse Events Cumulative to Week 2 by System	Safety (Subjects
14.3.1.4.5	Organ Class, Preferred Term, and Maximum Severity	Reaching Week 2)
	- 5	Safety (All Safety
	Number and Percentage of Subjects with Severe Treatment-	Subjects,
	Emergent Adverse Events Cumulative to Week 2 by System	Reaching Week 2
14.3.1.4.6	Organ Class, Preferred Term, and Maximum Severity	or Not)
14.5.1.4.0	Number and Percentage of Subjects with Treatment-Emergent	01 1101)
	Adverse Events Leading to Dose Interruption Cumulative to	
	Week 2 by System Organ Class, Preferred Term, and	Safety (Subjects
14.3.1.4.7	Maximum Severity	Reaching Week 2)
14.3.1.4.7	Number and Percentage of Subjects with Treatment-Emergent	Safety (All Safety
		• ` `
	Adverse Events Leading to Dose Interruption Cumulative to	Subjects,
142140	Week 2 by System Organ Class, Preferred Term, and	Reaching Week 2
14.3.1.4.8	Maximum Severity	or Not)
	Number and Percentage of Subjects with Treatment-Emergent	
	Adverse Events Leading to Dose Modification Cumulative to	G-f-t- (G 1 ' '
142140	Week 2 by System Organ Class, Preferred Term, and	Safety (Subjects
14.3.1.4.9	Maximum Severity	Reaching Week 2)
	Number and Percentage of Subjects with Treatment-Emergent	Safety (All Safety
	Adverse Events Leading to Dose Modification Cumulative to	Subjects,
	Week 2 by System Organ Class, Preferred Term, and	Reaching Week 2
14.3.1.4.10	Maximum Severity	or Not)
	Number and Percentage of Subjects with Treatment-Emergent	
	Adverse Events Leading to Study Discontinuation Cumulative	
	to Week 2 by System Organ Class, Preferred Term, and	Safety (Subjects
14.3.1.4.11	Maximum Severity	Reaching Week 2)
	Number and Percentage of Subjects with Treatment-Emergent	Safety (All Safety
	Adverse Events Leading to Study Discontinuation Cumulative	Subjects,
	to Week 2 by System Organ Class, Preferred Term, and	Reaching Week 2
14.3.1.4.12	Maximum Severity	or Not)
L	· · · · · · · · · · · · · · · · · · ·	

Version: 1.0 Page 37 of 51

	12. 1 12. 12. 14. The state of	T
	Number and Percentage of Subjects with Treatment-Emergent	
1.1.2.1.1.1.2	Adverse Events of Special Interest Cumulative to Week 2 by	Safety (Subjects
14.3.1.4.13	System Organ Class, Preferred Term, and Maximum Severity	Reaching Week 2)
		Safety (All Safety
	Number and Percentage of Subjects with Treatment-Emergent	Subjects,
	Adverse Events of Special Interest Cumulative to Week 2 by	Reaching Week 2
14.3.1.4.14	System Organ Class, Preferred Term, and Maximum Severity	or Not)
	Number and Percentage of Subjects with Anticholinergic	
	Treatment-Emergent Adverse Events Cumulative to Week 2	
	by System Organ Class, Preferred Term, and Maximum	Safety (Subjects
14.3.1.4.15	Severity	Reaching Week 2)
	Number and Percentage of Subjects with Anticholinergic	Safety (All Safety
	Treatment-Emergent Adverse Events Cumulative to Week 2	Subjects,
	by System Organ Class, Preferred Term, and Maximum	Reaching Week 2
14.3.1.4.16	Severity	or Not)
	Number and Percentage of Subjects with Treatment-Emergent	
	Adverse Events Cumulative to Week 4 by System Organ	Safety (Subjects
14.3.1.5.1	Class, Preferred Term, and Maximum Severity	Reaching Week 4)
		Safety (All Safety
	Number and Percentage of Subjects with Treatment-Emergent	Subjects,
	Adverse Events Cumulative to Week 4 by System Organ	Reaching Week 4
14.3.1.5.2	Class, Preferred Term, and Maximum Severity	or Not)
	Number and Percentage of Subjects with Treatment-Related	
	Treatment-Emergent Adverse Events Cumulative to Week 4	
	by System Organ Class, Preferred Term, and Maximum	Safety (Subjects
14.3.1.5.3	Severity	Reaching Week 4)
	Number and Percentage of Subjects with Treatment-Related	Safety (All Safety
	Treatment-Emergent Adverse Events Cumulative to Week 4	Subjects,
	by System Organ Class, Preferred Term, and Maximum	Reaching Week 4
14.3.1.5.4	Severity	or Not)
	Number and Percentage of Subjects with Severe Treatment-	
	Emergent Adverse Events Cumulative to Week 4 by System	Safety (Subjects
14.3.1.5.5	Organ Class, Preferred Term, and Maximum Severity	Reaching Week 4)
		Safety (All Safety
	Number and Percentage of Subjects with Severe Treatment-	Subjects,
	Emergent Adverse Events Cumulative to Week 4 by System	Reaching Week 4
14.3.1.5.6	Organ Class, Preferred Term, and Maximum Severity	or Not)
	Number and Percentage of Subjects with Treatment-Emergent	
	Adverse Events Leading to Dose Interruption Cumulative to	
	Week 4 by System Organ Class, Preferred Term, and	Safety (Subjects
14.3.1.5.7	Maximum Severity	Reaching Week 4)
	Number and Percentage of Subjects with Treatment-Emergent	Safety (All Safety
	Adverse Events Leading to Dose Interruption Cumulative to	Subjects,
	Week 4 by System Organ Class, Preferred Term, and	Reaching Week 4
14.3.1.5.8	Maximum Severity	or Not)
	Number and Percentage of Subjects with Treatment-Emergent	Safety (Subjects
14.3.1.5.9	Adverse Events Leading to Dose Modification Cumulative to	Reaching Week 4)

Version: 1.0 Page 38 of 51

	Week 4 by System Organ Class, Preferred Term, and	
	Maximum Severity	
14.3.1.5.10	Number and Percentage of Subjects with Treatment-Emergent Adverse Events Leading to Dose Modification Cumulative to Week 4 by System Organ Class, Preferred Term, and Maximum Severity	Safety (All Safety Subjects, Reaching Week 4 or Not)
14.3.1.5.11	Number and Percentage of Subjects with Treatment-Emergent Adverse Events Leading to Study Discontinuation Cumulative to Week 4 by System Organ Class, Preferred Term, and Maximum Severity	Safety (Subjects Reaching Week 4)
14.3.1.5.12	Number and Percentage of Subjects with Treatment-Emergent Adverse Events Leading to Study Discontinuation Cumulative to Week 4 by System Organ Class, Preferred Term, and Maximum Severity	Safety (All Safety Subjects, Reaching Week 4 or Not)
14.3.1.5.13	Number and Percentage of Subjects with Treatment-Emergent Adverse Events of Special Interest Cumulative to Week 4 by System Organ Class, Preferred Term, and Maximum Severity	Safety (Subjects Reaching Week 4)
14.3.1.5.14	Number and Percentage of Subjects with Treatment-Emergent Adverse Events of Special Interest Cumulative to Week 4 by System Organ Class, Preferred Term, and Maximum Severity	Safety (All Safety Subjects, Reaching Week 4 or Not)
14.3.1.5.15	Number and Percentage of Subjects with Anticholinergic Treatment-Emergent Adverse Events Cumulative to Week 4 by System Organ Class, Preferred Term, and Maximum Severity	Safety (Subjects Reaching Week 4)
14.3.1.5.16	Number and Percentage of Subjects with Anticholinergic Treatment-Emergent Adverse Events Cumulative to Week 4 by System Organ Class, Preferred Term, and Maximum Severity	Safety (All Safety Subjects, Reaching Week 4 or Not)
14.3.1.6.1	Number and Percentage of Subjects with Treatment-Emergent Adverse Events Cumulative to Week 6 by System Organ Class, Preferred Term, and Maximum Severity	Safety (Subjects Reaching Week 6)
14.3.1.6.2	Number and Percentage of Subjects with Treatment-Emergent Adverse Events Cumulative to Week 6 by System Organ Class, Preferred Term, and Maximum Severity	Safety (All Safety Subjects, Reaching Week 6 or Not)
14.3.1.6.3	Number and Percentage of Subjects with Treatment-Related Treatment-Emergent Adverse Events Cumulative to Week 6 by System Organ Class, Preferred Term, and Maximum Severity	Safety (Subjects Reaching Week 6)
14.3.1.6.4	Number and Percentage of Subjects with Treatment-Related Treatment-Emergent Adverse Events Cumulative to Week 6 by System Organ Class, Preferred Term, and Maximum Severity	Safety (All Safety Subjects, Reaching Week 6 or Not)
14.3.1.6.5	Number and Percentage of Subjects with Severe Treatment- Emergent Adverse Events Cumulative to Week 6 by System Organ Class, Preferred Term, and Maximum Severity	Safety (Subjects Reaching Week 6)

Version: 1.0 Page 39 of 51

		Safety (All Safety
	Number and Percentage of Subjects with Severe Treatment-	Subjects,
		Reaching Week 6
142166	Emergent Adverse Events Cumulative to Week 6 by System	_
14.3.1.6.6	Organ Class, Preferred Term, and Maximum Severity	or Not)
	Number and Percentage of Subjects with Treatment-Emergent	
	Adverse Events Leading to Dose Interruption Cumulative to	
	Week 6 by System Organ Class, Preferred Term, and	Safety (Subjects
14.3.1.6.7	Maximum Severity	Reaching Week 6)
	Number and Percentage of Subjects with Treatment-Emergent	Safety (All Safety
	Adverse Events Leading to Dose Interruption Cumulative to	Subjects,
	Week 6 by System Organ Class, Preferred Term, and	Reaching Week 6
14.3.1.6.8	Maximum Severity	or Not)
	Number and Percentage of Subjects with Treatment-Emergent	
	Adverse Events Leading to Dose Modification Cumulative to	
	Week 6 by System Organ Class, Preferred Term, and	Safety (Subjects
14.3.1.6.9	1 · · · · · · · · · · · · · · · · · · ·	Reaching Week 6)
14.3.1.0.9	Maximum Severity Number and Percentage of Subjects with Treatment Emorgent	
	Number and Percentage of Subjects with Treatment-Emergent	Safety (All Safety
	Adverse Events Leading to Dose Modification Cumulative to	Subjects,
	Week 6 by System Organ Class, Preferred Term, and	Reaching Week 6
14.3.1.6.10	Maximum Severity	or Not)
	Number and Percentage of Subjects with Treatment-Emergent	
	Adverse Events Leading to Study Discontinuation Cumulative	
	to Week 6 by System Organ Class, Preferred Term, and	Safety (Subjects
14.3.1.6.11	Maximum Severity	Reaching Week 6)
	Number and Percentage of Subjects with Treatment-Emergent	Safety (All Safety
	Adverse Events Leading to Study Discontinuation Cumulative	Subjects,
	to Week 6 by System Organ Class, Preferred Term, and	Reaching Week 6
14.3.1.6.12	Maximum Severity	or Not)
	Number and Percentage of Subjects with Treatment-Emergent	,
	Adverse Events of Special Interest Cumulative to Week 6 by	Safety (Subjects
14.3.1.6.13	System Organ Class, Preferred Term, and Maximum Severity	Reaching Week 6)
14.5.1.0.15	System Organ Class, Preferred Term, and Waximum Severity	Safety (All Safety
	Number and Percentage of Subjects with Treatment-Emergent	Subjects,
		_
1421614	Adverse Events of Special Interest Cumulative to Week 6 by	Reaching Week 6
14.3.1.6.14	System Organ Class, Preferred Term, and Maximum Severity	or Not)
	Number and Percentage of Subjects with Anticholinergic	
	Treatment-Emergent Adverse Events Cumulative to Week 6	
	by System Organ Class, Preferred Term, and Maximum	Safety (Subjects
14.3.1.6.15	Severity	Reaching Week 6)
	Number and Percentage of Subjects with Anticholinergic	Safety (All Safety
	Treatment-Emergent Adverse Events Cumulative to Week 6	Subjects,
	by System Organ Class, Preferred Term, and Maximum	Reaching Week 6
14.3.1.6.16	Severity	or Not)
	Number and Percentage of Subjects with Treatment-Emergent	Safety (Subjects
	Adverse Events Cumulative to Week 12 by System Organ	Reaching Week
